4.2. Statistical significance and confidence interval

As calculated in 4.1, we will consider a $P < 0.015$ as statistically significant for our primary outcomes. When we find a $0.015 \leq P \leq 0.05$, we will consider this association of dubious significance and will emphasise the increased chance of a type I error. Results will be presented with their values (e.g. regression coefficients, odds ratios, etc.) with 98.5% confidence intervals.

4.3. Adherence and protocol deviations

4.3.1. *Definitions of protocol deviations*

Protocol deviations are defined when the activities on a study diverge from the local institutional review board-approved protocol, however without significant consequences (13).

4.3.2. *Protocol deviations to be summarised*

We opted for the following subgroup analyses in our study protocol: different types of shock (distributive, obstructive, hypovolemic, cardiogenic), CVVH, heart failure by any cause, myocardial infarction, atrial fibrillation or surgery versus no-surgery patient groups.

We decided to replace these proposed subgroup analyses by the subgroups described in section 6.3. We believe that these subgroups agree better with the perspective from which a physician approaches a critically ill patient.

5. Study population

5.1. Screening data

Eligible patients who were not included will be compared to included patients by comparing their general characteristics (age, sex), and SAPS-II and APACHE-IV scores.

5.2. Eligibility

All eligible patients were included on their first day of ICU admission. Inclusion in the basic study consisted of a protocolised clinical examination and subsequent CCUS. The attending ICU physician estimated the expected duration of ICU treatment. Patients expected to stay beyond 24 hours who were eventually discharged within 24 hours were included in our main analyses.

5.2.1. Inclusion criteria

- Emergency admission
- Expected stay > 24 hours

5.2.2. Exclusion criteria

- Age < 18 years
- Planned admission (either after surgery or for other reasons)
- Unable to obtain informed consent, e.g. refusal, acute psychiatric disorders, mental retardation, serious language barriers
- Continuous resuscitation efforts or mechanical circulatory support

5.3. Recruitment

A flow diagram will be used to visualise the flow of patients. In this flow diagram, we will report the population from which the eligible patients were selected, reasons for exclusion of eligible patients, and how many CCUS images and measurements were validated (diagnostic study) or how many patients died (prognostic study). See **figure 1** for an example of our flow diagram.

5.4. Withdrawal/follow-up

5.4.1. Level and timing of withdrawal

The withdrawal rate of the SICS-I is below 2%, since it was an observational study in which no interventions were applied.

Following hospital regulations, patients or their legal representatives were informed and were excluded if they refused to participate. Withdrawal from our study occurred when informed consent was obtained from the patient's legal representative, but the patient refused at a later time.

5.4.2. *Reasons and details of withdrawal*

Reasons for withdrawal or lost to follow-up will be reported in the manuscript and/or flow diagram. Our observational study consists of a one-time measurement (snapshot), so that drop-outs or lost to follow-up reasons are unrelated to the study.

Patients who were lost to follow-up are considered alive until their last outpatient visit or hospital discharge, and were censored thereafter.

5.5. **Baseline patient characteristics**

5.5.1. *Collected baseline patient characteristics*

The cohort study was designed to register a set of clinical examination, biochemical and haemodynamic variables in each included patient. We extracted baseline demographic data from the Dutch National Intensive Care Evaluation (NICE) registry and collected clinical data by protocolised clinical examination and CCUS. We obtained the biochemical values from arterial blood gas analyses closest to study inclusion. **Table 2** provides an overview of all collected variables and indicates for each variable whether it is categorised as a clinical examination, haemodynamic, or biochemical variable.

5.5.2. *Descriptive summarization of baseline patient characteristics*

We will list general patient characteristics in a baseline characteristics table. Data will be presented as mean with standard deviation (SD) when normally distributed or as median with interquartile range in case of skewed data. Dichotomous and categorical data will be presented in proportions. Normality of the data will be assessed using P-P plots, Q-Q plots, and histograms. Linearity will be assessed using scatter plots. Differences between continuous variables will be assessed using Student's t-tests or Mann-Whitney-U test, depending on normality, whereas the Chi-squared test will be used for categorical values. For repeated measurements, we will use the paired t-test for normally distributed continuous data, the Wilcoxon signed-rank test for skewed continuous data, and the McNemar test for dichotomous data.

5.6. **Assumed confounding covariates**

The majority of variables measured in our study are inevitably correlated, as most relate to the haemodynamic status of a patient. While definitions have been recorded in the protocol, the values of the variables can be confounded by unmeasured factors, such as environmental, genetic, or psychological influences. Therefore, we provide an example of possible confounding variables and categorise these into 'measured' and 'unmeasured'.

- Cardiac output and clinical examination of the central haemodynamics (i.e. heart rate, blood pressures, central venous pressure) are assumed to be confounded by:
 - Measured: body surface area (therefore we will use cardiac index), quality of measurements (therefore data will be validated), distributive shock as the underlying pathology, administration of inotropes and/or vasopressors, administration of propofol (negative inotropic effect), mechanical ventilation including ventilation pressures
 - Unmeasured: stress, pain, anxiety
- Urine production is assumed to be confounded by:
 - Measured: history of chronic renal failure, distributive shock as the underlying pathology
 - Unmeasured: total amounts of fluids administered
- AVPU score is assumed to be confounded by
 - Measured: sedation (propofol, midazolam)
- Clinical examination of peripheral perfusion (i.e. mottling, peripheral capillary refill times, peripheral temperatures) are assumed to be confounded by:
 - Measured: heating blankets, distributive shock as the underlying pathology, cardiac output, administration of inotropes and/or vasopressors, administration of propofol (vasodilation)
 - Unmeasured: regular blankets, environmental temperature, peripheral arterial disease.
- Mortality proportion is assumed to be confounded by:
 - Measured: age, comorbidities, and several other variables that are all embedded in the simplified acute physiology score II (SAPS-II) score
 - Unmeasured: cause of mortality (e.g., death due to multi-organ failure or failure to wean, a patient's or family's personal wishes regarding the extent of ICU treatment. This will, however, always be a mix of causes).

We acknowledge that there will be residual confounding in our dataset due to the presence of unmeasured confounding, some of which is listed above. However, the actual measured variables reflect daily practice and so, is assumed to reflect similar confounding in daily assessments of the haemodynamic status of ICU patients.

6. Analysis

6.1. Outcome definitions

6.1.1. Primary and secondary outcomes

The research questions and the design of the study have been published (7). We elaborate on the outcomes of the basic study below and described the primary outcomes of each sub-study in appendix 1.

The outcomes of research question 1, i.e. the diagnostic study, are:

- Primary: the association of a single or combination of clinical examination findings with cardiac index measured by CCUS
- Secondary: the diagnostic test accuracy of a single or a combination of clinical examination findings to diagnose a low, normal and high cardiac index
- Secondary: the association and diagnostic test accuracy of a single or combination of clinical examination findings with cardiac index in clinically different patient subgroups

The outcomes of research question 2, i.e. the prognostic study, are:

- Primary: the association of all measured clinical examination, biochemical and haemodynamic variables with 90-day mortality
- Secondary: the association of clinical examination, biochemical and haemodynamic variables with 7-day and 30-day mortality
- Secondary: the association of clinical examination, biochemical and haemodynamic variables that are not visible to caregivers with 90-day mortality
- Secondary: the association of clinical examination, biochemical and haemodynamic variables with 90-day mortality in clinically different patient subgroups

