For the prognostic study we obtained follow-up on all-cause mortality from the municipal personal records database. Analysis of mortality will be performed using time-to-event data (patients were censored at 90-days of follow-up).

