Analysis of mortality will be performed using time-to-event data (patients were censored at 90-days of follow-up). Categorical variables will be analysed using the log-rank test and continuous variables will be assessed using a univariable Cox proportional hazard regression analysis. Analysis of mortality proportion will be presented by Kaplan-Meier survival curves when independent variables are dichotomous or categorical. A univariable Cox regression analysis will be conducted on 22 clinical examination, haemodynamic and biochemical variables with 90-day mortality as the dependent variable. Covariates with a $p < 0.25$ in the univariable analysis will be included in the multivariable model. We will include the SAPS-II score in our multivariable Cox regression model of 90-day mortality. The SAPS-II is a predictive score for in-hospital mortality and includes seventeen covariates among which age, haemodynamic and biochemical variables, and presence of metastatic or haematological cancer (21). The proportionality assumption will be tested by using the Schoenfeld and scaled Schoenfeld residuals. We will test the proportionality of the model as a whole and the proportionality for each predictor and reject proportionality in case of significant test findings ($p < 0.05$). We will plot graphs of the scaled Schoenfeld assumption, where horizontal lines in the graph indicate that the proportionality assumption is not violated. We will also construct log-log plots, where two parallel lines indicate that proportionality was not violated. The goodness of fit of the final model will be evaluated

by using the Cox-Snell residuals. In our Cox regression models, at least 15 events are necessary for each variable included in the final model (22,23).

6.2.4. *Validation (both)*

Because of the fixed sample size of our study, we will use bootstrapping validation to assess the accuracy of our model. We will randomly select 1075 individuals from the dataset with replacement, build our model on the bootstrapped sample and validate it on the original data. We will repeat this process 100 times and include a variable into our final model if it was significant in at least 80 models. We will still emphasise the hypothesis-generating aspect of our findings. We aim to validate our findings in an independent cohort in the future.

6.3. **Sensitivity and subgroup analyses**

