In the diagnostic study, we will conduct a sensitivity analyses on the subgroup of patients in which the quality of the cardiac output measurements by CCUS by the core laboratory is considered 'good'.

In the prognostic study, we will conduct a sensitivity analyses on different follow-up times of mortality: we will also use mortality at 7 and 30 days.

If the sample size permits, we will conduct subgroup analysis in different subpopulations. We will create the following subgroups in the basic study and test both our prognostic and diagnostic hypotheses on:

- Subgroup 1: subdivide the population into three groups: no shock, shock associated with a low cardiac output, shock associated with a high cardiac output.
- Subgroup 2: subdivide the population by underlying pathologies that could influence the haemodynamic measurements in a patient: Patients admitted due to cardiac arrest, heart failure, after liver transplantation or liver failure, central nervous system pathologies, and septic shock. We will identify clinical subgroups by using variables such as APACHE-IV admission diagnoses, confirmed infection, cardiac arrest from the Dutch National Intensive Care Evaluation (NICE) registry. The NICE registry contains good quality and complete data due to several assurance quality procedures (24). Patients with septic shock are identified using the quick Sequential Organ Failure Assessment (qSOFA) score combined with a confirmed infection according to the latest definition (25).

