6.6. Additional analyses: machine learning

6.6.1. *Model development: algorithms, training and testing*

We will use machine learning (ML) algorithms to generate hypotheses, validate observations of conventional models, and to unravel heterogeneity. Predictive modelling using ML algorithms requires the original data be split into two smaller sets, one for training and one for testing. We randomly split the original data into two groups with, respectively, 70 to 80% and 20 to 30% of the individuals. The split before further division of the training data into several folds for cross-validation virtually assures no information leakage is possible, making the training method virtually completely unbiased.

The training set will then be further divided into k similarly sized partitions (k -folds). By doing this, we divide the training set each time into k parts and then use each of these k parts once as testing dataset for the model trained on the other $k-1$. During this process, the hyper-parameters defining the model are optimized, with the performance measures (AUROC, accuracy, or a measurement of error, depending on whether the analysis is regression or classification) being presented as the average of those k runs of the algorithm. Additionally, this process can be repeated r number of times, where the average of r error terms obtained after performing k -fold cross validation r times is calculated.

This will be done for each of the algorithms, so as to determine the optimal values of all modifiable hyper-parameters of each model and maximize the models' performance metrics (usually the Area Under the Receiver Operating Characteristic curve (AUROC) for classification). When deemed

necessary, an additional post-hoc sensitivity analysis will be done to refine the parameters beyond what the tuning functions in R allow.

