The robust implementation of all three algorithms used to model ICU mortality prediction in the SICS-I database in the caret package used in R, allows us to obtain an importance-based ranking of the variables, with respect to their ability to predict the outcome variable. This feature is potentially applicable in clinical practice and provides an intuitive way to reduce the dimensionality (i.e. number of input variables). However, Principal Component Analysis (PCA) can be an even better tool to shed light on parameter prioritization for data-driven studies in the ICU.

PCA is an adaptive data analysis technique for reducing the dimensionality of large datasets, thus increasing interpretability, while simultaneously minimizing information loss. It identifies the largest sources of variation in a dataset and constructs a lower dimensional subspace of the data by creating new uncorrelated variables, or principal components (PCs), that successively maximize variance (43). To form each additional PC, it seeks a second linear combination that can explain the maximum of the remaining variance. For each PC, variable loadings are then provided, which represent the contribution of each original variable in explaining the variance in each of the PCs. Unlike predictive modelling, PCA is a descriptive tool, rather than inferential or predictive, which can partly substantiate or explain the predicted findings.

With iterative PCA, a variation on normal PCA, scores for both variables and individuals of complete or incomplete datasets are returned, providing an idea of the contribution of a certain variable, or a certain individual, to the total variance in that dataset (44). PPCA and BPCA are both iterative techniques with a probabilistic basis, which have been shown to perform better than traditional PCA when applied to data with missing values, especially as the missingness level increases (43). Using the

The R packages *factoextra* (45) and *factoMineR* (46), the PCA results are presented graphically by means of a graphic showing the distribution of individuals across a plane containing two PCs, a correlation circle graphic with the most explanatory variables or factors for each PC, and the PCA biplot showing a combination of both for clarity. The squared cosine (\cos^2) of the most relevant individuals and variables is also given, as is their percentual contribution (47).

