Serum leucocytes	B			X		
Serum hematocrit	B			X		
Serum thrombocytes	B			X		
Serum NT-proBNP	B			X		
Serum hs-troponin T	B			X		
Serum ASAT, ALAT	B			X		
Serum total and direct bilirubin	B			X		
Serum and urine creatinine	B, 8			X		
Serum and urine urea	B			X		
Serum and urine albumin	B			X		
Urine total volume and hours of collection	B, 8			X		
Follow-up						
Mortality in-ICU	All				X	
Mortality reason	All				X	
Mortality 7 day	All				X	
Mortality 30 day	All				X	
Mortality 90 day	All				X	

Table 3. Summary of the hyper-parameters of the three algorithms used for predictive modeling

Algorithm	Parameters	Definition
Gradient Boosted Machine	n.trees	Determines the number of trees (iterations) generated by the algorithm.
	n.minobsnode	Defines the minimum number of observations in the terminal nodes of a tree.
	interaction depth	Defines the number of terminal nodes or leaves of a tree.
	shrinkage	Controls the learning rate of the algorithm.
Random Forest	ntree	Defines the number of trees built by the algorithm.
	mtry	Defines the number of candidate variables randomly selected and tried at each split of a tree.
Support Vector Machine	cost (C)	Controls the misclassification tolerance.
	sigma (σ)	Defines how much a single training example influences the model (a higher sigma constrains the model towards linear).

10. References

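### The only mortality outcome named for the machine-learning models is ICU mortality, while the conventional models they are meant to help validate use 90-day mortality

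*SAP*

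**What the plan says.** **Conventional analysis.** Section 6.1.1 gives the primary prognostic outcome as "Primary: the association of all measured clinical examination, biochemical and haemodynamic variables with 90-day mortality". Other horizons enter as "Secondary: the association of clinical examination, biochemical and haemodynamic variables with 7-day and 30-day mortality". The remaining secondary outcomes (variables not visible to caregivers, and subgroups) are again at 90 days. Section 6.2.3 runs univariable Cox regression on "22 clinical examination, haemodynamic and biochemical variables with 90-day mortality as the dependent variable", and both 6.1.2 and 6.2.3 state that follow-up is censored at 90 days. Among the sensitivity analyses in 6.3, the only change of horizon is that "we will also use mortality at 7 and 30 days". The basic-study question in Table 1 names the same three horizons.

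**Machine learning.** Section 6.6.1 gives three purposes, one of which is to "validate observations of conventional models". Sections 6.6.3, 6.6.5 and 6.6.6 describe the outcome only as two classes, alive and deceased. Section 6.6.7, on principal component analysis, introduces the variable-importance rankings by referring to "all three algorithms used to model ICU mortality prediction in the SICS-I database".

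**Data collected.** The follow-up block of Table 2 has a row "Mortality in-ICU" and separate rows for death by 7, 30 and 90 days.

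**The concern.** A second method can support a first only if both address the same outcome. Here the conventional models count deaths to day 90, wherever they occur. The only mortality outcome named for the machine-learning models is ICU mortality, whose observation window ends at each patient's own ICU discharge.

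The section's main outputs for comparison are importance rankings and discrimination. If a variable ranks high in one analysis and low in the other, the reader could not tell whether the algorithm or the outcome made the difference. Agreement would be equally hard to read. The label also sets the proportion of patients classed as deceased. That proportion bears on the 0.50 classification threshold in 6.6.5 and on the option in 6.6.4 to select the model with a threshold method for imbalanced classes.

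**Working it through.** No arithmetic applies: the point depends on no sample size, error rate or event count. The check sets the outcome definitions side by side.

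| Place in SAP | Mortality outcome |
|---|---|
| 6.1.1, primary | 90 days |
| 6.1.1, secondary | 7 and 30 days; 90 days for the other secondary outcomes |
| 6.1.2 and 6.2.3, Cox model | 90 days, time to event |
| 6.3, sensitivity | 7 and 30 days |
| Table 1, basic study | 7, 30 and 90 days |
| 6.6.3, 6.6.5, 6.6.6, machine learning | alive or deceased, no time point |
| 6.6.7, machine learning | ICU mortality |
| Table 2, data collected | in-ICU, 7, 30 and 90 days, as separate rows |

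1. ICU mortality is absent from 6.1.1, 6.2.3 and 6.3. It appears as an outcome to be modelled only in 6.6.7.
2. Table 2 keeps in-ICU death apart from 90-day death, so within this plan they are different labels.
3. Applying 6.6.7 literally to three kinds of patient gives:

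| Patient | Cox model, 90 days | Machine learning, ICU label |
|---|---|---|
| Dies in the ICU before day 90 | event | deceased |
| Dies after ICU discharge, before day 90 | event | alive |
| Leaves the ICU and is alive at day 90 | no event | alive |

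The middle row carries opposite labels in the two analyses.

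4. Taking the phrase in 6.6.7 as loose wording instead leaves 6.6 with no time point at all, while Table 2 offers four mortality labels.
5. Number of patients in the middle row: the SAP gives no count of in-ICU deaths and no mortality rate for the whole cohort, so this cannot be computed.

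**The case against.** The case on the other side is substantial, and most of it stands.

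- **The wording is thin evidence.** One phrase, in an aside in the principal component subsection, carries the contradiction. SICS-I is a cohort of ICU patients, so the phrase may simply mean predicting mortality among ICU patients. Table 2 words its own variable slightly differently. This stands as a possible reading, but it does not settle the matter, because 6.6 then fixes no horizon.
- **The main validation lies elsewhere.** Section 6.2.4 validates both conventional models with 100 bootstrap samples and a rule that a variable must be significant in at least 80, and it looks ahead to an independent cohort. This stands. A reader might infer that the plan's validation as a whole fails, and the SAP does not support that.
- **The work is supplementary.** Section 6.6 is headed as additional analyses, and its first stated purpose is to generate hypotheses. No primary estimate, P-value or confidence interval depends on it. This also stands. A reader might infer that the prognostic results become uninterpretable. What is lost is only the use of the machine-learning models as a check on the conventional mortality models.
- **The size cannot be taken from the SAP's rates.** It is tempting to derive death counts from 0.28, 0.18 and 0.27. But 0.28 is a pilot 90-day rate among controls (Appendix 1, sections 4.5 and 11.5), 0.18 is a pilot 30-day rate among controls, and 0.27 is the hypothetical alternative in the power calculation (both in 3.2.2). Multiplying or subtracting them does not give deaths in this cohort.

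Section 6.1.1 itself is clear and agrees with 6.1.2, 6.2.3 and 6.3. The defect is in 6.6.

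**Conclusion.** The point holds in a limited form. The mortality label in 6.6 is either ICU mortality, which does not match the analysis it is meant to support, or it is not fixed in time. In both cases the machine-learning results cannot serve as validation of the 90-day findings as the plan is written. The mislabelling of deaths after ICU discharge follows only if 6.6.7 is read literally. The absence of a horizon follows on the looser reading.

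The consequence is confined to the supplementary machine-learning work. The number of patients with opposite labels is unknown. Section 7 says the SAP was drafted to guard against outcome reporting bias and data-driven results, and an open choice among four recorded mortality labels works against that aim. It should be corrected, but it does not block the primary analysis.

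**What to change.** - In 6.6, state that the label for the mortality models, the ensembles and the importance rankings is all-cause mortality at 90 days, from the municipal records named in 6.1.2. Correct the phrase in 6.6.7 to match.
- Report how many patients were censored before day 90 under 5.4.2 and how the classifiers handle them. Leaving them out is simple but may slightly bias predicted risk, because it removes patients known to be alive up to their censoring date. The text should say so.
- Acknowledge that a binary label and a censored time-to-event outcome still differ after this change, so the comparison is closer but not exact.
- If ICU mortality is what is intended, list it as an additional exploratory outcome and drop the validation claim for it.

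The cost is a few sentences in the SAP. Mortality at 90 days is already among the follow-up variables in Table 2, so no new data are needed. Sections 6.6.2 and 6.7 describe parts of the machine-learning work in the past tense. If models have already been fitted to an ICU label, the exploratory models would need to be re-run.
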